Prior to leaving the clinic, subjects will be scheduled for their next visit (Week 3, \pm 2 days) and reminded to refrain from using their oral hygiene products for 12 hours and refrain from eating, chewing gum, drinking (small sips of water will be allowed up to 45 minutes), and tobacco use for 4 hours prior to their next visit.

Any Adverse Events or general comments will be recorded on the appropriate eCRF. All serious AEs will be reported. As for non-serious AEs, only voluntarily reported whole body adverse events that are potentially product related will be reported as will all oral related Adverse Events.

Week 3 (\pm 2 day):

Subjects will return to the site and bring their test products. Continuance criteria will be assessed and recorded on the appropriate eCRF. Subjects will then receive Oral Examination, MGI, and GBI assessments (in that order) by the experienced examiner. Following that, subjects will swish their mouth with disclosing solution and the same experienced examiner will conduct a pre-brushing plaque exam: Turesky Modified Quigley-Hein Index (TQHPI).

Any Adverse Events or general comments will be recorded on the appropriate eCRF. All serious AEs will be reported. As for non-serious AEs, only voluntarily reported whole body adverse events that are potentially product related will be reported as will all oral related Adverse Events.

Subject accountability will be recorded on the appropriate eCRF and subjects will be dismissed from the study. Subjects must return all test products in order to be exited from the study.

4. Inclusion Criteria

In order to be included in the study, each subject must:

- give written informed consent and receive a copy of the signed Informed Consent form;
- be at least 18 years of age;
- typically use a manual toothbrush;
- be in good general health as determined by the investigator/designee based on a review/update of their medical history;
- possess a minimum of 16 scorable teeth (excluding third molars) with facial and lingual scorable surfaces;
- have a Baseline MGI score between 1.75 and 2.5;
- have a Baseline TQHPI score of at least 2.00;
- have a Baseline between 20 and 80 Bleeding sites;
- abstained from all oral hygiene procedures for approximately 12 hours prior to this visit and agree to do the same prior to the subsequent visit;

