9	Missing tooth

Examiner: [name], RDH, BSEd, MS

14. Hypothesis

The following hypotheses will be investigated for each efficacy endpoint at Week 3:

Gingivitis Hypothesis:

Null Hypothesis: There is no difference between treatment groups with respect to the mean GI change from baseline (MGI, GBI, or number of bleeding sites) at 3 weeks when an adjustment is made for the respective baseline GI score.

Alternative Hypothesis: There is a difference between the treatment groups with respect to mean GI change from baseline (MGI, GBI, or number of bleeding sites) at 3 weeks when an adjustment is made for the respective baseline GI score.

Plaque Hypothesis:

Null Hypothesis: There is no difference between treatment groups with respect to the mean TQHPI change from baseline at 3 weeks when an adjustment is made for baseline TQHPI score.

Alternative Hypothesis: There is a difference between the treatment groups with respect to mean TQHPI change from baseline at 3 weeks when an adjustment is made for baseline TQHPI score.

15. Statistical and Analytical Plans

Statistical analyses for gingivitis efficacy will be based on whole-mouth average MGI, GBI, and number of bleeding sites change from baseline scores (Baseline minus Week 3). An ANCOVA will be performed to determine treatment differences on the whole mouth average gingivitis reduction with the respective baseline gingivitis score as the covariate. Baseline by treatment interaction will be investigated and included in the final ANCOVA model if significant at the 10% level. Separate analyses will be performed for each gingivitis endpoint with MGI being primary.

Statistical analyses for plaque efficacy will be based on average whole mouth TQHPI change from baseline score (Baseline minus Week 3). The 3-week plaque reduction will be analyzed for treatment differences using an ANCOVA with baseline whole mouth TQHPI score as the covariate. Baseline by treatment interaction will be investigated and included in the final ANCOVA model if significant at the 10% level.

The within-treatment differences from baseline gingivitis scores (MGI, GBI, number of bleeding sites) will be tested versus zero using a paired difference t-test. Similar within-treatment analyses will be carried out for TQHPI.

The lingual and buccal surfaces of the gingivitis and plaque endpoints will be analyzed separately for treatment differences as described above.

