If the data does not satisfy the normality criterion, transforming the data or analogous nonparametric methods will be employed. Additional analyses may also be performed in order to more fully understand the data. All treatment comparisons will be considered two-sided with an $\alpha=0.10$ significance level.

Demographic and baseline variables will be summarized by treatment group, and adverse events reported or noted during the study will be documented and listed by treatment group.

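### Does Section 15 leave the primary MGI test open when the baseline-by-treatment interaction is kept?

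*Combined protocol and SAP*

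**What the plan says.** Section 15 analyses change from baseline (baseline minus Week 3) by ANCOVA "to determine treatment differences on the whole mouth average gingivitis reduction with the respective baseline gingivitis score as the covariate". It then adds the conditional step: "Baseline by treatment interaction will be investigated and included in the final ANCOVA model if significant at the 10% level". On the ranking of endpoints it says: "Separate analyses will be performed for each gingivitis endpoint with MGI being primary". The conditional sentence appears again for TQHPI. The surface-level analyses inherit it: "The lingual and buccal surfaces of the gingivitis and plaque endpoints will be analyzed separately for treatment differences as described above".

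Section 14 states the gingivitis hypotheses for the mean change from baseline "when an adjustment is made for the respective baseline GI score". Section 15 sets the level: "All treatment comparisons will be considered two-sided", at 0.10. Section 4 bounds the covariates: participants must "have a Baseline MGI score between 1.75 and 2.5" and "have a Baseline TQHPI score of at least 2.00", with 20 to 80 bleeding sites. Section 11 gives 15 per arm, a number chosen on logistical grounds, and Section 2 calls the study exploratory.

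No section gives a baseline value, or names a test, for comparing the arms once the interaction is in the model.

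**The concern.** With a common slope, the treatment difference is one number. With separate slopes it is a straight line over baseline, and a treatment test needs either a point on that line or a joint hypothesis about all of it. Three readings can be constructed:

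1. the adjusted difference at the overall mean baseline;
2. a joint 2-df test of treatment and interaction;
3. the treatment coefficient with uncentred baseline, which is the difference at baseline 0.

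They can disagree. If slopes are truly equal, about one trial in ten keeps the interaction by chance, and in those trials the primary p-value could depend on which reading is used. If the choice were made after seeing the data, the stated 10% level would not be guaranteed. The same sentence governs TQHPI, the other gingivitis endpoints and the surface analyses, so the question recurs in every between-arm efficacy comparison.

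**Working it through.** **Inputs from the documents.** 15 per arm (Section 11); two-sided 0.10 for the treatment test and 10% for keeping the interaction (Section 15); baseline MGI from 1.75 to 2.5 (Section 4).

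**Assumptions.** No treatment effect, equal slopes, normal residuals. Three shapes for baseline MGI within the entry range: uniform; normal with mean 2.1 and SD 0.15, truncated; normal with mean 2.35 and SD 0.10, truncated. There were 200,000 simulated trials per shape. The Monte Carlo standard error is √(0.10 × 0.90 / 200,000) = 0.07 points near 10%.

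**Formulas.** With arm means x̄ and ȳ, arm slopes b, within-arm sums of squares S and residual SD s, the interaction model gives

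D(c) = [ȳ₁ + b₁(c − x̄₁)] − [ȳ₀ + b₀(c − x̄₀)],

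SE = s√[2/15 + (c − x̄₁)²/S₁ + (c − x̄₀)²/S₀], on 26 df.

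If the interaction is not significant, the common-slope ANCOVA on 27 df is used.

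**Results (% of trials).**

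| | Uniform | Mean 2.1 | Mean 2.35 |
|---|---|---|---|
| Common-slope ANCOVA always | 9.99 | 9.97 | 9.99 |
| Interaction kept | 9.93 | 10.00 | 9.98 |
| Rule, overall mean baseline | 10.22 | 10.20 | 10.22 |
| Rule, joint 2-df test | 14.52 | 14.44 | 14.50 |
| Rule, MGI 0 | 18.18 | 18.44 | 18.67 |

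The first row reproduces the plan's 10%.

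**Where the differences arise.** Only the kept branch differs between readings. For the uniform shape, rejection within that branch is 12.15% at the mean, 55.5% for the joint test and 92.36% at MGI 0.

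- Branch contribution at the mean: 0.0993 × 0.1215 = 0.0121. The other branch therefore contributes 0.1022 − 0.0121 = 0.0901.
- Joint test: 0.0993 × 0.555 + 0.0901 = 0.0551 + 0.0901 = 0.1452.
- MGI 0: 0.0993 × 0.9236 + 0.0901 = 0.0917 + 0.0901 = 0.1818.

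**Why MGI 0 behaves so badly.** For a uniform baseline the variance is 0.75²/12 = 0.0469, so S is about 14 × 0.0469 = 0.656 per arm, and the mean is 2.125. In units of the residual variance, D(0) has variance 2/15 + 2 × 2.125²/0.656 ≈ 0.13 + 13.76 = 13.90. The slope difference has variance 2/0.656 = 3.05, and their covariance is −2 × 2.125/0.656 = −6.48. The correlation is −6.48/√(13.90 × 3.05) = −0.995. The coefficient at 0 therefore nearly repeats the interaction test that has just been passed. Its standard error is about √13.90/√0.133 = 10 times that at the mean. At the overall mean baseline the covariance is zero when the two arms have equal S, so passing the interaction test says little about the treatment difference there.

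**Which reading the text supports.** Because D(c) is linear, its value at the overall mean baseline equals its average over all enrolled participants. That is a baseline-adjusted difference in mean change, which is what Section 14 states. The joint test has a different null: no difference at any baseline, including equal slopes. MGI 0 lies 1.75 units below the lowest eligible score.

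**Other endpoints, at the mean baseline, under assumed distributions.** TQHPI 10.2–10.3%; bleeding sites 10.2–10.4%. With 13 per arm, MGI gives 10.3–10.4%. GBI was not calculated because the documents give no baseline range for it.

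**The case for a change.** The strongest counter-argument is that a test should be fixed by the text and not by what an analyst would probably do. The joint test is a respectable procedure, and the wording does not forbid it. Nor is inflation confined to an absurd baseline of 0: evaluating at an edge of the entry range gives 14.9–17.9%, and fixing MGI at 2.125 gives 10.4–16.0%, the top figure arising when baselines cluster well above that value. If slopes truly differed by 0.5 residual SD per baseline SD (an assumption), about 35% of trials would enter the branch, not 10%. With an assumed true benefit of 1 residual SD and no interaction, the coefficient at 0 would significantly favour control in 29–33% of the trials that keep the interaction.

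Some of this stands. The text is silent on the baseline value, and one clause naming the overall mean baseline would settle it at no cost. The rest carries less weight. An edge or an arbitrary fixed value is not what an adjusted mean difference denotes, and nothing in the documents points to one. The reversal figure is conditional: about 0.10 × 0.29 to 0.10 × 0.33, or 3% of all trials, and only if the coefficient at 0 is used. Truly different slopes make the branch more common, but the mean-baseline comparison still estimates the average difference that Section 14 asks about.

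**Conclusion.** The concern identifies a real silence but not a defect that needs a change. On the reading that Sections 14 and 15 support, the false-positive rate for MGI is 10.2% against the stated 10%, and it barely moves across the baseline shapes tried. The figures of 14.5% and 18% depend on tests that fit the stated hypothesis poorly. A clause naming the mean baseline would only record what a competent analyst would do.

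Dropping the conditional step in favour of a fixed common-slope model would gain about 10.2 − 10.0 = 0.2 points. It would also give up modelling different slopes where they exist, and the sponsor may fairly prefer to keep that in an exploratory study of 30 participants. The conclusion rests on normal residuals, equal slopes under the null and the assumed baseline distributions. It was not checked numerically for GBI.

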Even in extreme plaque accumulation conditions, thorough oral hygiene and mechanical plaque removal is reported to reduce gingivitis and restore health. Control of supra gingival plaque is an essential element in effective oral hygiene programs. Oral hygiene devices are under continuous review for efficacy and safety, as new devices or improvements of features on existing devices are developed.

2. Study Objective

The primary objective of this exploratory study is to evaluate the efficacy of an Oral Irrigator in the reduction of gingivitis compared to a negative control over a 3 week period by using the Modified Gingival Index and the Gingival Bleeding Index.

The secondary objective is to evaluate the efficacy of an Oral Irrigator in the reduction of plaque compared to a negative control using the extended Turesky Modified Quigley-Hein Index (TQHPI) after 3 weeks of use.

3. Overall Study Design and Plan

This is a single-center, examiner-blind, three (3) week, two (2) treatment, parallel group, randomized study design. Thirty (30) subjects who have shown evidence of gingivitis and plaque will be enrolled in this study. Subjects will be evaluated for gingivitis using the Modified Gingival Index (MGI) and the Gingival Bleeding Index (GBI) and evaluated for plaque using the Turesky Modified Quigley-Hein Plaque Index (TQHPI) at two (2) time points: Baseline and after three (3) weeks of product use. Prior to each visit (Baseline and Week 3) subjects will be instructed to abstain from brushing and performing any oral hygiene 12 hours prior and to abstain from eating, drinking (small sips of water will be allowed up to 45 minutes prior to the visit), chewing gum and tobacco use for four (4) hours prior to the visits.

Qualified subjects will be stratified and randomly assigned to one of the two treatment groups, toothbrushing on conjunction with an Oral Irrigator or toothbrushing without an Oral Irrigator, (N=15/treatment) based on Baseline gingivitis (MGI) score, Baseline whole mouth mean TQHPI score, Baseline number of bleeding sites, and tobacco use. Subjects will be given product use instructions and asked to perform a supervised usage of their assigned products. Subjects will be instructed to brush twice a day for approximately three (3) weeks with their assigned products and return for plaque and gingivitis measures at approximately three (3) weeks after the Baseline visit. Specific procedures are detailed below (Table 1).

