Changes to the Protocol following IRB approval affecting the safety of subjects, scope or objectives of the investigation, or the scientific quality of the study will be documented as amendments. Such changes will require the Sponsor, Investigator, and IRB approval prior to implementation, unless immediate action is required to safeguard subject safety. Administrative or minor changes (e.g., typographical errors, changes in Sponsor personnel, etc.) will be documented as revisions but may not need to be submitted as amendments unless required by the IRB. Any change in the Sponsor's monitoring staff, Clinical Trial Manager or Medical Monitor during the conduct of the study, will be reported to the Investigator.

Good Clinical Practices

This study is classified non-AMG, non-MPG according to German study classification but conducted in compliance with applicable sections of the US Federal Regulations governing informed consent (21 CFR 50) and IRBs (21 CFR 56). The conduct of this study will be in accordance with ICH-GCPs as published by the FDA, with the Commission Directive 2005/28/EC published by the European Union, and ISO 14155:2011. During the course of the trial, the clinical site will allow monitoring by the Sponsor (Clinical Trial Manager or designee) to check compliance with the Protocol, regulations and guidelines, adequacy of the equipment and facilities, and satisfactory data collection.

Institutional Review

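### Do Sections 2 and 15 leave the primary gingivitis endpoint undecided between MGI and GBI?

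*Combined protocol and SAP*

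**What the plan says.** Section 2 (Study Objective) opens: "The primary objective of this exploratory study is to evaluate the efficacy of an Oral Irrigator" in reducing gingivitis, "compared to a negative control over a 3 week period by using the Modified Gingival Index and the Gingival Bleeding Index". The two indices are not ranked. Plaque (TQHPI) is the only secondary objective, so GBI has no other place among the objectives.

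Section 14 (Hypothesis) is a template: "The following hypotheses will be investigated for each efficacy endpoint at Week 3". Its gingivitis hypothesis covers MGI, GBI and number of bleeding sites, and marks none of them as deciding.

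Section 15 (Statistical and Analytical Plans) specifies an ANCOVA of change from baseline with the respective baseline score as covariate, then states: "Separate analyses will be performed for each gingivitis endpoint with MGI being primary". It closes with the decision level: "All treatment comparisons will be considered two-sided", at alpha 0.10.

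Section 11 sets 15 subjects per group on logistical grounds. The documents give no effect size, standard deviation or correlation between the indices.

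**The concern.** Read alone, Section 2 puts GBI on the same footing as MGI, while Section 15 puts it below. No sentence links the two, and none says whether the primary objective is met by MGI alone, by both indices or by either. Section 14 does not help, and number of bleeding sites is missing from the objectives altogether.

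What would be at stake is the headline result. If MGI reached significance and GBI did not, Section 15 would give a positive primary result, but a reading of Section 2 that needs both would not. If only GBI reached significance, Section 15 would give a negative result, but a reading that accepts either would not. With 15 per arm such splits are a realistic outcome, and an undefined primary result could be settled after the data are seen.

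**Working it through.** **Step 1. Set the sections side by side.**

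| Element of a decision rule | Section 2 | Section 14 | Section 15 |
|---|---|---|---|
| Measures named | MGI, GBI | MGI, GBI, number of bleeding sites | MGI, GBI, number of bleeding sites |
| Which one is primary | silent | silent | MGI |
| Model | silent | baseline adjustment | ANCOVA, respective baseline |
| Level | silent | silent | two-sided 0.10 |
| Rule combining indices | silent | silent | none; separate analyses |

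Only Section 15 fills every element needed for a decision. Section 2 contradicts none of them; it says what gingivitis will be measured with. The plan as written therefore yields one rule: MGI, ANCOVA, two-sided p<0.10. Number of bleeding sites is not a stray endpoint: Section 13 B has the examiner record the gingival units that bleed during the same examination that gives GBI.

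**Step 2. Error rate when neither index has an effect.** The plan gives no figure to reproduce, so this step is illustrative. For two tests at two-sided 0.10 with correlation r between the test statistics, P(either) = 1 − P(both |z| < 1.645) and P(both) = 0.20 − P(either). The correlations are assumptions.

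| r | MGI alone | Either | Both |
|---|---|---|---|
| 0 | 0.10 | 1 − 0.9² = 0.190 | 0.010 |
| 0.3 | 0.10 | 0.185 | 0.015 |
| 0.5 | 0.10 | 0.176 | 0.025 |
| 0.7 | 0.10 | 0.161 | 0.039 |
| 0.9 | 0.10 | 0.136 | 0.064 |

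The rule actually written has the nominal 10% rate.

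**Step 3. How often a rival reading would change the answer.** Inputs: 15 per arm (Section 11), ANCOVA with 27 residual df (30 − 3), two-sided 0.10 (Section 15), and an assumed standardised effect of 0.8 on both indices. Simulation with 40,000 draws, counting significance in favour of the irrigator:

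| r | MGI alone | Both | Either | MGI only (0.68 − both) | GBI only | Any split (either − both) |
|---|---|---|---|---|---|---|
| 0.3 | 0.68 | 0.495 | 0.860 | 0.185 | 0.182 | 0.365 |
| 0.5 | 0.68 | 0.525 | 0.830 | 0.155 | 0.154 | 0.306 |
| 0.7 | 0.68 | 0.555 | 0.797 | 0.125 | 0.122 | 0.242 |

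A rule needing both differs from Section 15 only when MGI alone is significant. A rule accepting either differs only when GBI alone is. Each column is about 12–18%. The 24–36% in the last column compares the two unwritten rules with each other, so it is not the rate at which either departs from the plan.

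**Step 4. Sensitivity.** At r = 0.9 and effect 0.8, the normal approximation gives power Φ(0.8 × √7.5 − 1.645) = 0.7075 per index and 0.646 for both, so each departure is 0.7075 − 0.646 = 0.06. Simulation puts the total split at about 0.14, or 0.14 / 2 = 0.07 each. Halving the simulated split at r = 0.3, 0.5 and 0.7:

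- effect 0.5: 0.384, 0.323, 0.248 become 0.19, 0.16, 0.12;
- effect 1.0: 0.234, 0.204, 0.158 become 0.12, 0.10, 0.08.

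**The case for a change.** The best argument for a change is that an objective naming two indices, with nothing saying that one is only supportive, ought to match the endpoint that decides it. No sentence says Section 15 prevails over Section 2. An exploratory label does not excuse leaving the headline open to choice, and at effect 0.8 the chance of success would run from about 50% (both, r = 0.3) to 86% (either, r = 0.3).

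The textual part stands: Section 2 does not rank the indices, and a sentence there calling GBI supportive would read better. The rest carries less weight. The 50% and 86% belong to rules that the plan does not contain; the written rule gives 68%. The choice is not open either, because MGI is designated primary in the plan, so promoting GBI afterwards would be a visible departure from Section 15. The study promises no familywise control, so no error guarantee is broken.

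Rewording the objective also has a cost. The Appendix (Protocol Amendments/Changes) requires Sponsor, Investigator and IRB approval for "Changes to the Protocol following IRB approval affecting the safety of subjects, scope or objectives of the investigation". If the rewording also made the buccal and lingual analyses descriptive, it would remove treatment comparisons that Section 15 plans, which has nothing to do with ranking MGI and GBI.

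**Conclusion.** The concern does not call for a change. The mismatch is a missing cross-reference between a general objective and a specific analysis section, and a competent analyst resolves it one way: MGI change from baseline decides, while GBI and number of bleeding sites are analysed separately and reported alongside it. Aligning Section 2 would restate that rule without altering the primary analysis, its 10% two-sided error rate or the sample size.

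The size of the issue, if someone did impose a rule needing both indices or accepting either, is about 12–18% of trials for each at an assumed effect of 0.8 and correlation of 0.3–0.7, and about 6–7% at correlation 0.9. These figures assume equal standardised effects on both indices. The documents supply neither effects nor correlations, so they show scale only. The conclusion itself rests on the text of Sections 2, 14 and 15.
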